## JHM IRB - eForm A – Protocol

- Use the section headings to write the JHM IRB eForm A, inserting the appropriate material in each. If a section is not applicable, leave heading in and insert N/A.
- When submitting JHM IRB eForm A (new or revised), enter the date submitted to the field at the top of JHM IRB eForm A.

\*\*\*\*\*  
\*\*\*\*\*

### 1. Abstract

Ventricular tachycardia (VT), a life-threatening fast heart rhythm, occurs frequently in patients with myocardial infarction, leading to sudden cardiac death. Catheter-based ablation, the delivery of energy to destroy the ability of cardiac tissue to conduct electrical signals, offers the possibility of permanent cure by interrupting the VT reentrant circuit. Unfortunately, eliminating infarct-related VT with ablation has achieved only modest success, 50-88%, and with complication rates as high as 8% of the treated population. This stems from limitations in current electrical mapping techniques used to identify the target locations for ablation. These include limited sampling during mapping, with resolution often insufficient to identify critical arrhythmia circuits, the hemodynamic intolerance during VT induction, and the ambiguities in correlating electrical maps with heart anatomy. Furthermore, the complex three-dimensional pathways of cardiac impulse propagation around/through the zone of infarct during VT are difficult to reconstruct by mapping the ventricular surfaces only. These limitations translate into inaccurate ablation targets and extensive unnecessary lesions, and into prolonged duration of the procedure, dramatically increasing the risk of chamber injury, thromboemboli, bleeding, and radiation overexposure. Our Hopkins team has developed a novel “virtual-heart” methodology that could eliminate the need for invasive electrical mapping in determining the optimal targets for infarct-related VT ablation. The approach is based on cardiac imaging and computational modeling, and is personalized to each patient. The methodology involves constructing three-dimensional computer models from patients’ CMR data. We then execute simulations with each virtual heart to evaluate all possible patient-specific VTs, and to determine automatically, using a novel algorithm, the optimal ablation targets that render, with minimum lesion size, each heart not inducible for VT.. The approach thus targets termination not only of VTs that are clinically manifested or induced at the time of procedure, but of all VTs that could arise from the given post-infarction substrate, including those that might arise following initial ablation, thus potentially eliminating the need for repeated ablations and offering long-term freedom from VT.

### 2. Objectives (include all primary and secondary objectives)

The goal of this study is to test the efficacy of the new imaging/simulation (“virtual heart”) approach for determining the optimal ablation sites in patients with VT, which render post-

infarction VT non-inducible. The study will test both the acute outcome of the ablation procedure, and the effect the use of the predicted targets has upon procedure time.

**3. Background** (briefly describe pre-clinical and clinical data, current experience with procedures, drug or device, and any other relevant information to justify the research)

We use a novel “virtual-heart” methodology that could eliminate the need for invasive electrical mapping in determining the optimal targets for ablation of VT in structural heart disease. The approach is based on cardiac imaging and computational modeling, and is personalized to each patient. The methodology involves constructing three-dimensional (3D) models of the patient’s ventricles, including all structural remodeling from patients’ clinical MRI data. We then execute simulations with each virtual heart to evaluate all possible patient-specific VTs, and to determine automatically, using a novel algorithm, the optimal ablation targets that render, with minimum lesion size, each heart not inducible for VT. The approach thus targets termination not only of VTs that are clinically manifested or induced at the time of procedure, but of all VTs that could arise from the given arrhythmogenic substrate, including those that might arise following initial ablation, thus potentially eliminating the need for repeated ablations and offering long-term freedom from VT. Retrospective studies have demonstrated an excellent correspondence between predicted targets in patients with VT and the lesions that successfully terminated VT. The methodology for constructing the patient’s 3D virtual heart and assessing the arrhythmogenic propensity of the substrate has been published by our team in *Nature Communications*. May 10;7:11437. doi: 10.1038/ncomms11437, 2016.

Once all possible VT that the arrhythmogenic substrate can sustain are determined, in each personalized virtual heart we determine the minimum-size (i.e. optimal) ablation lesions that render it not inducible for VT from any pacing location. These optimal targets are determined using a novel automatic algorithm we developed and validated recently (*Heart Rhythm* 13, 1687-1698, doi:10.1016/j.hrthm.2016.04.009 (2016)). The algorithm represents reentrant wave propagation as a flow network and identifies the smallest amount of tissue that, when eliminated from the network, disrupts and terminates the flow.

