**4. Study Procedures**

a. Study design, including the sequence and timing of study procedures (distinguish research procedures from those that are part of routine care).

1. Potential participants will be obtained from the Johns Hopkins Hospital electrophysiology lab inpatient and outpatient schedule and from the Johns Hopkins outpatient cardiac electrophysiology clinic, who have a planned procedure for catheter ablation of ventricular tachycardia.
2. Participants will undergo written consent.
3. The participant will then undergo a cardiac MRI scan performed with a 1.5-T MRI scanner, with delayed late gadolinium enhancement. Cardiac MRIs or CTs are part of the routine care at Johns Hopkins among patients presenting for a ventricular tachycardia catheter ablation.
4. MRIs should be acquired no more than 30 days and no fewer than 24 hours prior to a scheduled ablation procedure. If the patient has prior MRI data available matching the specified image parameters, from fewer than 30 days prior to the procedure, those data may be used instead.
5. The cardiac MRI will then be processed and simulations performed with each virtual heart to evaluate all possible patient-specific VTs, and to determine the optimal ablation targets.
6. In the event that a patient is enrolled, but a satisfactory, good quality MRI cannot be obtained, the patient will remain enrolled, but the guided ablation procedure will not be performed and the patient will undergo a standard ablation procedure. Other than this

notation of data, the procedure will be the same as if the subject were not enrolled in the study.

7. If a good quality cardiac MRI is obtained and a virtual heart model with the ablation targets is generated, the operating physician will merge the virtual heart lesion map to the invasive electroanatomical navigation system. After the patient has been catheterized, an attempt should be made to induce VT. The physician should then navigate the catheter to each of the ablation targets specified, and place a lesion as per his or her training and experience, confirming when done that the lesion marker in the mapping system coincides with the target. This will be done for each lesion.

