8. Once ablation lesions have been delivered at all of the suggested targets as described above, an attempt should be made once again to induce ventricular tachycardia, and the result recorded. If the operator feels the virtual heart guided ablation is an area to be unsafe, then no ablation will be performed.
9. Following the investigational portion of the procedure, the operator will continue to perform the rest of the VT ablation procedure per their discretion.

b. Study duration and number of study visits required of research participants.

We expect to enroll 10 participants over a one year period. Only two study visits would be required at this time, and this will coincide with the participant's normal pre procedure cardiac MRI study and catheter ablation procedure.

c. Blinding, including justification for blinding or not blinding the trial, if applicable.

This study is not blinded as the goal is to determine the acute procedural outcome of the inability to induce ventricular tachycardia.

d. Justification of why participants will not receive routine care or will have current therapy stopped.

The participants will receive routine care in regards to catheter ablation for the management of their arrhythmia.

e. Justification for inclusion of a placebo or non-treatment group.

There will be no placebo group.

f. Definition of treatment failure or participant removal criteria.

Participant failure would occur if the virtual heart modeling was unable to be performed secondary to a poor cardiac MRI study.

g. Description of what happens to participants receiving therapy when study ends or if a participant's participation in the study ends prematurely.

N/A

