### **Secondary Endpoints**

The secondary endpoints are how many additional lesions were needed to terminate VT, if any, and procedure duration.

- a. We anticipate that 10 participants will be adequate to describe the association of the virtual heat guided ablation lesions and acute VT non inducibility.
- b. Early stopping rules. We anticipate no untoward effects from this research. However, if any adverse events are noted the study will be terminated.

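### The protocol sets out to test an effect on procedure time, but with one guided group and no reference it can only describe that time

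*Protocol*

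**What the plan says.** Section 2 (Objectives) names two things that the study will test: the acute outcome of the ablation, and "the effect the use of the predicted targets has upon procedure time". In section 7, time appears among the secondary endpoints: "The secondary endpoints are how many additional lesions were needed to terminate VT, if any, and procedure duration".

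On the size and structure of the study, section 4b says "We expect to enroll 10 participants over a one year period". Under section 4a, step 7, patients with a good MRI and a completed model have the predicted targets ablated. Under step 6, if the MRI is not good enough, the patient stays enrolled but "the guided ablation procedure will not be performed and the patient will undergo a standard ablation procedure". Section 4f classes that case as a failure: "Participant failure would occur if the virtual heart modeling was unable to be performed secondary to a poor cardiac MRI study". Section 4e says there is no placebo group.

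On what time might be compared with, section 1 says that the limits of current mapping translate "into prolonged duration of the procedure", and section 9 hopes for shorter procedures. Neither gives a duration.

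**The concern.** An effect on time is a difference between the time with the predicted targets and the time without them. The protocol provides only the first of these. One of the two aims in section 2 therefore cannot be met by the design described.

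What is at stake is the claim made at the end. If the aim stays worded as a test of an effect, a mean duration from a handful of guided patients may be read as evidence that guidance shortens or lengthens the procedure. Any reference brought in after the durations are known would be open to selection.

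**Working it through.** **1. Is there a comparator for time?** The possible sources, taken in turn:

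| Possible source | What the protocol provides |
|---|---|
| Concurrent control group | None. All patients with a usable MRI and model are guided (section 4a, step 7) |
| Historical series or reference duration | None named in any section |
| Figure for current practice | Sections 1 and 9 speak of long and shorter procedures without a number |
| Within-patient baseline | Exists for inducibility (attempted at step 7 before the lesions and at step 8 after them). None for time, since each patient contributes one procedure |
| Enrolled but unguided patients | Only those whose MRI failed (step 6). Their number is unplanned, they are selected on image quality, and the protocol does not propose them as controls |

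With no value for time without the targets, the difference is undefined. A larger sample does not change this.

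**2. The plan's own sample size.** Section 7 regards 10 participants as enough to describe how the guided lesions relate to non-inducibility. It gives no calculation, and this rationale does not mention time. There is no figure for time to reproduce.

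**3. What the data can say about time (illustration).** The protocol gives no SD for duration, so results are in SD units. The half-width of the 95% confidence interval for the mean duration in n guided patients is t(0.975, n−1)/√n.

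- n = 10: 2.262/3.162 = 0.715 SD
- n = 8: 2.365/2.828 = 0.836 SD (this assumes 2 MRI failures among the 10; the protocol gives no expected number)

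**4. What a named reference set would add (illustration).** With n guided and m reference procedures and equal SDs assumed, the half-width for the difference in means is t(0.975, n+m−2)·√(1/n + 1/m). The detectable difference is for 80% power at two-sided 5%, from the noncentral t distribution. The values of m are assumptions.

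| Guided v reference | √(1/n + 1/m) | Half-width (SD) | Detectable difference (SD) |
|---|---|---|---|
| 10 v 20 | 0.387 | 0.79 | 1.12 |
| 10 v 50 | 0.346 | 0.69 | 0.99 |
| 10 v 100 | 0.332 | 0.66 | 0.94 |
| 8 v 50 | 0.381 | 0.76 | 1.09 |

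With an unlimited reference set, the normal approximation gives (1.960 + 0.842)/√10 = 0.886 SD. This is the limit set by having 10 guided patients.

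For an assumed SD of 45 to 90 minutes, 10 v 50 gives a half-width of 0.693 × 45 = 31 to 0.693 × 90 = 62 minutes, and a detectable difference of 0.987 × 45 = 44 to 0.987 × 90 = 89 minutes. A reference set would support an estimate with a wide interval, not a sensitive test.

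**The case against.** The strongest reply is that this is a small single-centre study with time as a secondary endpoint. Section 7 lists duration with no hypothesis, threshold or decision rule, so the mismatch comes down to one phrase in section 2. That limits the consequence and makes the fix cheap. The phrase still states an aim that the design cannot meet.

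A second reply is that an SAP, not available here, could name a historical reference. That is possible. However, the aim and the single guided group are fixed in the protocol, and the two do not match there. Start and stop points and time stamps may properly sit in an SAP or on the data forms, and their absence is not part of this point.

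A reader might go further and infer that total duration is itself an invalid measure. After the re-induction at step 8, "Following the investigational portion of the procedure, the operator will continue to perform the rest of the VT ablation procedure per their discretion", and section 8 says that the study adds one induction attempt and may add lesions. The documents do not support that inference:

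- In section 8, the possible extra lesions follow from ablating the predicted sites first. Time spent on them is part of the effect of using those targets, not a rival explanation. The same section expects fewer lesions than usual if the hypothesis is right.
- Total duration, discretionary work included, is a legitimate outcome for a strategy of ablating the predicted targets first. If guidance works, less should remain to be done.
- The extra induction is one among several usually made, and no figure suggests that it changes total time materially.

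Nor does the point reach the primary endpoint, which has its own before-and-after comparison.

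**Conclusion.** The point holds in this form: section 2 promises a test of an effect on procedure time, and the protocol supplies no reference against which an effect could be estimated. This conclusion follows from the design alone and needs no assumption about variability or sample size.

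What can be reported is the duration in at most 10 guided patients, with a 95% half-width of about 0.72 SD at 10 and 0.84 SD at 8. These figures assume a t interval for the mean. The comparisons with a reference set also rest on assumed reference sizes and equal SDs, and the minutes on an assumed SD.

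It should be corrected, because it changes what the study may conclude about time. It does not call the study as a whole into question.

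**What to change.** Either of two changes to section 2 resolves it.

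1. **Restate the time objective as describing procedure time.** Report total duration in the guided patients with its confidence interval. This costs a change of wording.
2. **Name a reference in advance.** Fix a set of earlier VT ablations from the same laboratory, with the same eligibility and the same start and stop definitions. Report the difference in total duration as a non-randomised estimate with its confidence interval. This costs data extraction and depends on such durations being retrievable. The protocol does not show that they are, and section 4a says routine imaging may be MRI or CT, so eligible earlier patients may be fewer than expected.

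Under either option, patients whose MRI failed should not serve as the comparison. The downside is a weaker claim about time: descriptive, or non-randomised with a wide interval. Care, the number of inductions and the sample size do not change.

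An optional addition concerns step 8, which asks that "an attempt should be made once again to induce ventricular tachycardia, and the result recorded". Noting the clock time as well, if it is not already captured, would let guided-phase time be shown beside total time. This would be descriptive only and does not supply the missing comparator.

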**4. Study Procedures**

a. Study design, including the sequence and timing of study procedures (distinguish research procedures from those that are part of routine care).

1. Potential participants will be obtained from the Johns Hopkins Hospital electrophysiology lab inpatient and outpatient schedule and from the Johns Hopkins outpatient cardiac electrophysiology clinic, who have a planned procedure for catheter ablation of ventricular tachycardia.
2. Participants will undergo written consent.
3. The participant will then undergo a cardiac MRI scan performed with a 1.5-T MRI scanner, with delayed late gadolinium enhancement. Cardiac MRIs or CTs are part of the routine care at Johns Hopkins among patients presenting for a ventricular tachycardia catheter ablation.
4. MRIs should be acquired no more than 30 days and no fewer than 24 hours prior to a scheduled ablation procedure. If the patient has prior MRI data available matching the specified image parameters, from fewer than 30 days prior to the procedure, those data may be used instead.
5. The cardiac MRI will then be processed and simulations performed with each virtual heart to evaluate all possible patient-specific VTs, and to determine the optimal ablation targets.
6. In the event that a patient is enrolled, but a satisfactory, good quality MRI cannot be obtained, the patient will remain enrolled, but the guided ablation procedure will not be performed and the patient will undergo a standard ablation procedure. Other than this

notation of data, the procedure will be the same as if the subject were not enrolled in the study.

7. If a good quality cardiac MRI is obtained and a virtual heart model with the ablation targets is generated, the operating physician will merge the virtual heart lesion map to the invasive electroanatomical navigation system. After the patient has been catheterized, an attempt should be made to induce VT. The physician should then navigate the catheter to each of the ablation targets specified, and place a lesion as per his or her training and experience, confirming when done that the lesion marker in the mapping system coincides with the target. This will be done for each lesion.
8. Once ablation lesions have been delivered at all of the suggested targets as described above, an attempt should be made once again to induce ventricular tachycardia, and the result recorded. If the operator feels the virtual heart guided ablation is an area to be unsafe, then no ablation will be performed.
9. Following the investigational portion of the procedure, the operator will continue to perform the rest of the VT ablation procedure per their discretion.

b. Study duration and number of study visits required of research participants.

We expect to enroll 10 participants over a one year period. Only two study visits would be required at this time, and this will coincide with the participant's normal pre procedure cardiac MRI study and catheter ablation procedure.

c. Blinding, including justification for blinding or not blinding the trial, if applicable.

This study is not blinded as the goal is to determine the acute procedural outcome of the inability to induce ventricular tachycardia.

d. Justification of why participants will not receive routine care or will have current therapy stopped.

The participants will receive routine care in regards to catheter ablation for the management of their arrhythmia.

e. Justification for inclusion of a placebo or non-treatment group.

There will be no placebo group.

f. Definition of treatment failure or participant removal criteria.

Participant failure would occur if the virtual heart modeling was unable to be performed secondary to a poor cardiac MRI study.

g. Description of what happens to participants receiving therapy when study ends or if a participant's participation in the study ends prematurely.

N/A

## 5. Inclusion/Exclusion Criteria

Patients that exhibit monomorphic VT secondary to scarring will be eligible for the study. Patients with implanted cardiac devices may also be enrolled based on standard protocol in the Radiology Departments at Johns Hopkins University. Due to the use of gadolinium as an MRI contrast agent, patients with GFR < 30 mL/min should not be enrolled in the study.

### Inclusion Criteria

Patients must meet all of the following inclusion criteria:

- Eligible patients must be at least 18 years old at the time of enrollment.
- A Pre-Op cardiac MRI including LGE must be performed prior to ablation. As JHU performs MRIs with ICD or pacemaker implanted, patients with these devices may be enrolled.
- Eligible patients must suffer from VT, thought to be secondary to structural heart disease (scarring).

- Eligible patients must be determined to be suitable candidates for ablation to treat VT by their cardiologist and/or electrophysiologists regardless of this protocol.

### **General Exclusion Criteria**

- Patients with GFR < 30 mL/min should not be enrolled in the study due to the use of intravenous gadolinium as an MRI contrast agent
- If a pre-procedure MRI cannot or likely will not be performed for any reason (such as claustrophobia), the patient must be excluded.
- Pregnant women may not participate in the study because gadolinium MRI contrast is contraindicated in these patients.
- Any subject that, during the course of the pre-procedure imaging, is discovered to have VT not related to scarring, he/she must be de-enrolled from the study.

## **6. Drugs/ Substances/ Devices**

N/A

## **7. Study Statistics**

### **Primary Endpoint**

The primary endpoint of this study is conversion from acute inducibility of VT to acute non-inducibility of VT using only the lesions indicated by our methodology.

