## **8. Risks**

### **Ablation Risks**

Standard ablation procedures include all of the operations that will be performed as part of the study, including induction of VT and termination of VT, pace mapping, and creation of lesions via radiofrequency energy. The study requires one additional attempt to induce VT, out of multiple attempts typically done during such a procedure. The study requires that the ablating physician ablate the predicted lesion sites first. If the hypothesis of this trial is correct, the number of lesions delivered will be smaller than usual. It is possible that several lesions might be added to the total number normally done during such a procedure. However, frequently multiple lesions are placed during such a procedure.

The acute harm associated with induction of ventricular tachycardia is patient hemodynamic instability. The acute harm associated with ablation lesions are in line with the risk of the procedure which includes pain, damage to heart valve, lung or heart perforation which could require emergency intervention or surgery, heart block, stroke or TIA, pulmonary embolism, myocardial infarction, phrenic nerve paralysis and death.

There is no clear long term harm from induction of ventricular tachycardia during an electrophysiology procedure. The long term harm associated with unnecessary ablation lesions in areas of diseased myocardial tissue is not clear.

In order to minimize risk, all procedures will be performed with cardiac anesthesiology support. Throughout the procedure, continuous hemodynamic monitoring including non-invasive/invasive measurements of blood pressure, heart rate, oxygen saturation and respiratory status will be performed. Ablation will only be performed by an experienced operator, using tools approved for the indication on diseased tissue which is important in the substrate for ventricular tachycardia.

All adverse events related to an electrophysiology procedure at the Johns Hopkins Hospital is recorded in a HIPAA secure RedCap database. Adverse events are assessed at the time of the procedure and at each subsequent clinic visit. Any unanticipated problems involving risk to subjects or others will be reported to FDA within 10 working days after receiving notice of the adverse effect.

Major complications are defined as life-threatening, leading to permanent harm, or necessitating intervention or prolonged hospitalization within 30 days of ablation.

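### Does a conversion endpoint require the protocol to demand inducible VT at entry, a written baseline result and an identical induction method before and after?

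*Protocol*

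**What the plan says.** The primary endpoint (Protocol, section 7) is "conversion from acute inducibility of VT to acute non-inducibility of VT using only the lesions indicated by our methodology". It needs two observations in the same patient: VT induced before the guided lesions, and VT not induced after them.

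The procedure is in section 4a. Step 7 covers the first observation: "After the patient has been catheterized, an attempt should be made to induce VT". The operator then goes to the predicted targets. Step 8 covers the second: "an attempt should be made once again to induce ventricular tachycardia, and the result recorded".

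Section 5 sets eligibility by clinical history: "Patients that exhibit monomorphic VT secondary to scarring will be eligible for the study". The listed criteria likewise ask for VT attributed to scar and for suitability for ablation. None asks that VT be inducible.

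The study has one arm, is not blinded (section 4c) and plans 10 participants (sections 4b and 7a). Section 7a says this number is adequate to describe an association. It gives no test, target rate or precision.

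**The concern.** A conversion can occur only in a patient who starts inducible, and the entry criteria do not guarantee that. Step 7 sends the operator on to the targets whatever the first attempt shows, and only step 8 mentions recording. No passage says that the two attempts use the same method, and the operator is not blinded. Sections 4c and 7a describe the outcome as the end state alone. The abstract lists "the hemodynamic intolerance during VT induction" and section 8 says "The acute harm associated with induction of ventricular tachycardia is patient hemodynamic instability", which suggests that some attempts may not be completed.

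If all this were left open, three things could go wrong. A patient who was never inducible might be credited to the guided lesions. A re-test that was not completed might be read as negative. A less searching second attempt might look like a treatment effect. In a single-arm study of 10, the before-and-after comparison is the main evidence of efficacy, and an induction badly done or not recorded cannot be recovered later.

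**Working it through.** **The plan's own figure.** The only figure is 10 participants. It comes with no error rate, power, target rate or precision, so there is no calculation to reproduce.

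**The passages side by side**

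1. *Scoring.* Section 7 defines success as a change. A patient not induced at step 7 has not changed state, whatever step 8 shows, and so is not a success. Section 4c explains why the study is not blinded and section 7a justifies the sample size. Neither defines the endpoint.
2. *Recording.* The endpoint cannot be scored without the step 7 result, so that result has to be kept. Naming the record only at step 8 is an uneven piece of drafting.
3. *Method.* Step 8 refers back to the earlier attempt, in the same patient and the same procedure. Section 8 counts VT induction among the operations of standard ablation, with several attempts usual. Leaving the technique to the operators' practice fits that description.
4. *Incomplete attempts.* The abstract names intolerance as a limit of current electrical mapping. Section 8 names instability as a harm of inducing VT. A patient who becomes unstable in induced VT has been induced, so the result is clear. Neither passage describes an attempt abandoned without a result.
5. *Clinical versus induced VT.* The abstract's phrase "VTs that are clinically manifested or induced at the time of procedure" describes which arrhythmias the model is meant to cover. It does not say that some enrolled patients will be non-inducible.
6. *Poor MRI.* Step 6 of section 4a keeps such a patient in the study without guided ablation, and section 4f counts the case as a failure. Both can hold, and neither bears on inducibility.

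**Size if the wrong reading were used.** The inputs are assumptions, because the protocol gives no rates. Let m of 10 be never inducible and c convert, with c + m = 8 non-inducible at re-test.

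- Bare non-inducibility: (c + m)/10 = 80% in every row.
- Conversion over all enrolled: c/10.
- Conversion among the baseline-inducible: c/(10 − m), with exact (Clopper-Pearson) 95% interval.

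| m | c/10 | c/(10 − m) | 95% interval | Width | 80% minus c/(10 − m) |
|---|---|---|---|---|---|
| 0 | 80% | 8/10 = 80.0% | 44.4 to 97.5 | 53 points | 0 points |
| 1 | 70% | 7/9 = 77.8% | 40.0 to 97.2 | 57 points | 2.2 points |
| 2 | 60% | 6/8 = 75.0% | 34.9 to 96.8 | 62 points | 5.0 points |
| 3 | 50% | 5/7 = 71.4% | 29.0 to 96.3 | 67 points | 8.6 points |

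Against the all-enrolled denominator the gap is m/10, or 10 points per never-inducible patient. Against the baseline-inducible denominator it is 2 to 9 points for m = 1 to 3, inside intervals of more than 50 points.

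**Could such patients occur?** If 10%, 20% or 30% are non-inducible at baseline (assumed), the chance of at least one in 10 is 1 − 0.9¹⁰ = 65%, 1 − 0.8¹⁰ = 89% or 1 − 0.7¹⁰ = 97%. So they may well occur, but the endpoint already says how to score them.

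**Precision lost.** If every evaluable patient converts, the lower 95% limit is 0.025^(1/n): 69% for n = 10, 66% for 9, 63% for 8 and 59% for 7.

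**Differing methods.** The documents give nothing from which to size this. As a reference, suppose the lesions had no effect and the second attempt re-induced VT with probability 95%, 90% or 80% (assumed). The expected false conversions among 10 inducible patients are then 10 × (1 − probability) = 0.5, 1 or 2. That is imperfect repeatability of the test, and a rule to use one method would not by itself remove it.

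**The case for a change.** The best case for a change is that conduct and data capture belong in the protocol. A SAP can choose a denominator afterwards. It cannot restore a baseline result that nobody wrote down or make two differently performed inductions comparable. The operator is unblinded, there is no control arm, and the remedy would cost only a sentence or two and two fields on a form.

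Part of this stands. Inducibility is not an entry requirement, step 7 has no branch for a patient who is not induced, recording is expressly requested only at step 8, and a common method is implied but not stated. Consistency of method is also the one element that a SAP could not repair.

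It does not carry the conclusion. Losing the baseline result would mean leaving out half of the study's own primary endpoint, and nothing in the protocol suggests that. Counting a never-inducible patient as a success would depart from section 7. No passage points to different methods being used, and no effect of doing so can be sized. What remains (the denominator, results that cannot be assessed, the evaluable number) is ordinarily settled in a SAP, which may exist but is not at hand.

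**Conclusion.** No change to the plan follows. The protocol leaves detail unwritten, but its endpoint definition already settles the question that matters: without VT induced at the start there is no conversion. The investigators need the first result in order to score the endpoint, and the natural reading of step 8 is a repeat of step 7.

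On assumed inputs (8 of 10 non-inducible at re-test, 0 to 3 of them never inducible), the wrong reading would overstate conversion by 0 to 9 points against the baseline-inducible and by 0 to 30 points against all enrolled. If all patients are inducible, the readings agree. The protocol describes 10 patients and sets no test or threshold that these differences could tip.

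The conclusion assumes that the step 7 result is kept, as the endpoint demands, and that both attempts are made in the operators' usual way. A document showing otherwise would reopen the point.
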